10 STATISTICAL CONSIDERATIONS

10.1 Statistical Hypotheses

The study has two primary endpoints: (i) Sustained resolution of COVID-19 signs and symptoms in all subjects (with Mild or Moderate disease at baseline); and (ii) Sustained resolution of COVID-19 signs and symptoms in subjects with Mild disease at baseline. The only hypothesis testing in

this study will be carried out for these two endpoints for which the single dose of the RD-X19 device will be compared with Sham based on the Final Cohort.

10.2 Power and Sample Size:

The target number of subjects to be randomized initially is 60 individuals seronegative for SARS-CoV-2 Spike IgG antibodies (20 subjects to each of two RD-X19 treatment arms and 20 subjects for Sham control). At the sponsors option, the total number of subjects can be increased to enroll up to 150 additional subjects to include all serostatuses based on adequate safety/tolerability observed in the final dose cohort. As described in Section 4.1.2 the RD-X19 dose to be used for the final cohort is determined based only on blinded data from Cohorts A and B.

Based on findings in the EB-P12-01 and the hazard ratio observed for the median time to sustained symptom resolution in the proof of concept trial, the option to increase the sample size with an anticipated roughly equal number of antibody positive to negative individuals in the final cohort has at least 90% power in the modified full analysis set (mFAS) population with the ability to detect meaningful changes in SARS-CoV-2 symptom resolution from baseline (Hazard ratio of 0.4 between active RD-X19 and Sham observed in EB-P12-01).

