  - Who have RR  $\geq 20$  at Baseline
  - Who report Shortness of Breath at Baseline, or
  - Who have clinical signs suggestive of lower airway involvement.
- 3) gender
- 4) age (grouping of <50,  $\geq 50$ )
- 5) baseline antibody status (positive, negative)

Note: For the second primary efficacy endpoint the term for baseline disease status of mild vs. moderate will not be included.

Two-sided 95% confidence intervals and two-sided 90% confidence intervals will also be derived for the hazard ratios from the above models.

Supportive analyses in each case for the two primary efficacy endpoints will be produced for the mFAS and the Per Protocol population. For the mFAS population the Cox proportional hazards regression model will not include the covariate related to baseline antibody status.

All of the above analyses of the primary endpoints will also be produced for pooled RD-X19 doses vs. pooled Sham, and for RD-X19 low dose (i.e., the dose not expanded to produce the Final Cohort) vs. Pooled Sham, but where in all cases these p-values will be viewed as descriptive only. For the analyses of pooled RD-X19 vs. pooled Sham the log-rank test and the Cox proportional hazards models will each be stratified by cohort.

Following notations are used in the sample SAS code:

- TRT: treatment group with values 1 for RD-X19 from Final Cohort, 2 for RD-X19 from Cohort A, and 3 for Sham from Final Cohort, 4 for Sham from Cohort A
- TRTpooL: value 12 for pooled RD-X19 from both cohorts, 3 for pooled Sham
- COHORT: A for first cohort, B for Final cohort
- HOURS: time to sustained resolution of COVID-19 signs and symptoms
- CNSR: the censoring variables, 1 for censored, 0 for not censored
- COVIDSEV: grouping of COVID-19 Composite Severity Score at baseline, 1 for score <1.25, 2 for score  $\geq 1.25$
- DSSTATUS: baseline disease status, 1 for mild, 2 for moderate
- SEX: 1 for males, 2 for females
- AGEGRP: grouping of age, 1 for age <50, 2 for age  $\geq 50$
- ANTIBODY: grouping of baseline antibody status, 1 for positive, 2 for negative

Sample SAS Code for Main Analysis

1. Unstratified analysis of Primary Endpoint 1: Time to sustained resolution of COVID-19 signs and symptoms (in mild and moderate subjects)

a) RD-X19 from Final Cohort vs Sham from Final Cohort, log-rank test (unstratified)

```
PROC LIFETEST DATA=datain CONFTYPE=LINEAR;  
  WHERE trt in (1,3);  
  TIME hours*cnsr(1);  
  STRATA trt/ TEST=LOGRANK;  
RUN;
```

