**PROC LIFETEST DATA=**data**in PLOTS=SURVIVAL(FAILURE);**  
    **WHERE trt in (1,3);**  
    **TIME hours\*cnsr(1);**  
    **STRATA trt;**  
**RUN;**

### 5.5.2 Analysis of Secondary and Exploratory Endpoints

All secondary clinical, virologic, and exploratory efficacy endpoints will be summarized using descriptive statistics by visit (as appropriate) for each treatment group.

For virologic outcome assessments, subjects without a Baseline biospecimen collected and/or the Baseline biospecimen determined to NOT be an analysis-qualified sample, will be excluded from these analyses.

Analysis-qualified samples are defined as nasopharyngeal and saliva SARS-CoV-2 biospecimen samples that have no sample Violations as outlined in the Biospecimen Violation and Biospecimen Deviation (BVBD) Log. Any samples that are not analysis-qualified, designated by “Valid biospecimen = N” will be replaced by missing values (prior to the multiple imputation described below).

Viral load (log base 10 copies/mL) and cycle threshold (Ct) data are continuous in nature but may be reported as “undetermined” or “inconclusive” or “<LOQ”.

For analysis-qualified samples, results of “undetermined” and “<LOQ” for N1 copies/mL will be handled as follows for data summary purpose:

- For viral load reported as “Undetermined”, value 1 will be used to calculate descriptive statistics. This will support the need for logarithm transformation.
- For viral load reported as “<LOQ”, value  $5 \times 10^1$  will be used to calculate descriptive statistics.

Sample values reported as either “Inconclusive” N1 Ct viral load or with an “Undetermined” RNase P (RP) internal control Ct value will be replaced by missing values prior to the multiple imputation (MI) described below.

MI will be performed separately for saliva samples and nasopharyngeal samples and for each treatment via a two-step process for subjects with non-missing baseline. Viral load values will be log10-transformed before MI. Missing data occurring for an intermediate visit will be imputed first using a Markov Chain Monte Carlo (MCMC) method. As a result, a monotone missingness pattern will be obtained for the data to be fully imputed. The subsequent imputation will use Monotone Regression to produce 100 imputed datasets where the remaining missing data are filled in.

The SAS code for MI is as follows:

- Saliva samples: random number = 184962 as the seed for the first Step and 64849 as the seed for the second step.

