- Nasopharyngeal samples: random number = 133274 as the seed for the first Step and 485044 as the seed for the second step.

Where notation of main variables:

- Log\_dayX: log10-transformed viral load at Day X visit, where X=1, 3, 5, 8 and 14.

\*Step 1: MCMC fills interim missingness to make monotone;

```
PROC MI data=datain out=step1 seed=XXXXXX n impute=100;
  mcmc impute=monotone;
  var log_day1 log_day3 log_day5 log_day8 log_day14;
run;
```

\*Step 2: MI regression;

```
PROC MI data=step1 out=step2 seed=XXXXXX n impute=1
  var log_day1 log_day3 log_day5 log_day8 log_day14;
  monotone reg(log_day3 = log_day1); *for D3;
  monotone reg(log_day5 = log_day1 log_day3); *for D5;
  monotone reg(log_day8 = log_day1 log_day3 log_day5); *for D8;
  monotone reg(log_day14 = log_day1 log_day3 log_day5 log_day8);
  by _imputation_;
run;
```

If either of the above multiple imputation procedures fails to converge, then multiple imputation (for both calls to PROC MI) will only be carried out for the Final Cohort, in which case only one of the 3 dummy variables for treatment will be needed in the first call to PROC MI.

The imputed values will be converted back to original scale by raising 10 to the power. For each missing value, its geometric mean of the 100 MI copies will be derived prior to the calculation of the summary statistics.

For log10-transformed viral load data, geometric means will be computed by exponentiating (base 10) the group means of the log10-transformed viral load.

In conjuncture with above handling of the viral data scenarios, for purposes of this protocol, clearance of viral infection post baseline visit is defined as achievement of: [1] RP Ct  $\geq 0$ , AND [2] Average N1 Ct = “Undetermined”.

Subjects with missing nasopharyngeal samples at any post baseline visit will not be imputed for the purposes of determining the proportion of subjects demonstrating clearance of viral infection. Such cases will be determined to be a ‘failure’ at this visit/assessment as having not achieved the endpoint of clearance of viral infection. If a subject’s nasopharyngeal SARS-CoV-2 biospecimen sample at Visit X had a Violation as outlined in the Biospecimen Violation and Biospecimen Deviation Log, the subject will also be considered ‘FAILURE’ at Visit X.

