Table 14.2.3.1.1 – Summary of Secondary Virologic Outcomes: Log10-Transformed Nasopharyngeal Viral Load by Visit for Subjects with Mild and Moderate Disease at Baseline, Full Analysis Set

Study Visit	Statistics	RD-X19 from Final Cohort	RD-X19 from Cohort A	Pooled RD-X19	Pooled Sham
Visit 1 / Day 1	N	XX	XX	XX	XX
	Mean ± SD	XX.X ± XX.X	XX.X ± XX.X	XX.X ± XX.X	XX.X ± XX.X
	Median	XX.X	XX.X	XX.X	XX.X
	Min, Max	XX, XX	XX, XX	XX, XX	XX, XX
	Geometric Mean on Original Scale	XX.X	XX.X	XX.X	XX.X
Visit 2 / Day 3	N	XX	XX	XX	XX
	Mean ± SD	XX.X ± XX.X	XX.X ± XX.X	XX.X ± XX.X	XX.X ± XX.X
	Median	XX.X	XX.X	XX.X	XX.X
	Min, Max	XX, XX	XX, XX	XX, XX	XX, XX
	Geometric Mean on Original Scale	XX.X	XX.X	XX.X	XX.X
Visit 3 / Day 5					
Visit 4 / Day 8					
Visit 5 / Day 14					

To deal with missing data multiple imputation (MI) has been carried out on the Log10 scale. The mean of the 100 MI copies is used in each case to replace the missing value. Summary statistics are calculated after this imputation for missing data.

Note: Geometric Means are computed by exponentiating (base 10) the Means of the log10-transformed viral load.

Source: Listing 16.x.x

O:\Studies\EmitBio\EB-P20-01\Biometrics\Programs\Tables\xxx.sas ran on Month Day, Year at hh:mm on data from Month Day, Year.

Repeat Table 14.2.3.1.1 for the following:

Table 14.2.3.1.2 – Summary of Secondary Virologic Outcomes: Log10-Transformed Nasopharyngeal Viral Load by Visit for Subjects with Mild Disease at Baseline, Full Analysis Set

Repeat Tables 14.2.3.1.1 and 14.2.3.1.2 for the following:

Table 14.2.3.2.1 – Summary of Secondary Virologic Outcomes: Log10-Transformed nasopharyngeal Viral Load by Visit for Subjects with Mild and Moderate Disease at Baseline, Modified Full Analysis Set

Table 14.2.3.2.2 – Summary of Secondary Virologic Outcomes: Log10-Transformed nasopharyngeal Viral Load by Visit for Subjects with Mild Disease at Baseline, Modified Full Analysis Set

Table 14.2.3.3.1 – Summary of Secondary Virologic Outcomes: Log10-Transformed Nasopharyngeal Viral Load by Visit for Subjects with Mild and Moderate Disease at Baseline, Per-Protocol Population

Table 14.2.3.3.2 – Summary of Secondary Virologic Outcomes: Log10-Transformed Nasopharyngeal Viral Load by Visit for Subjects with Mild Disease at Baseline, Per-Protocol Population

Table 14.2.4.1 – Summary of Secondary Virologic Outcomes: Proportion of Subjects with Clearance of Viral Infection by Visit for Subjects with Mild and Moderate Disease at Baseline

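### Averaging the 100 imputed viral loads before summarising makes the tabulated log10 SDs too small, and the SAP gives conflicting accounts of treatment in the imputation model (descriptive tables only).

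*SAP*

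**What the plan says.** Protocol 10.4 and SAP 5.2.1 single out missing post-baseline viral load for multiple imputation. SAP 5.5.2 sets out two PROC MI steps with 100 imputations, then adds: "For each missing value, its geometric mean of the 100 MI copies will be derived prior to the calculation of the summary statistics". The shells for nasopharyngeal load (Table 14.2.3.1.1) and saliva load (Table 14.2.5.1) say the same on the log10 scale: "The mean of the 100 MI copies is used in each case to replace the missing value". N, mean ± SD, median, minimum, maximum and geometric mean then come from that one filled-in dataset.

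On treatment, SAP 5.5.2 gives three accounts:

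- Prose: "MI will be performed separately for saliva samples and nasopharyngeal samples and for each treatment via a two-step process".
- Non-convergence fallback: imputation is restricted to the Final Cohort, and "only one of the 3 dummy variables for treatment will be needed in the first call to PROC MI".
- Printed code: the variable list in both calls is "var log_day1 log_day3 log_day5 log_day8 log_day14", with no treatment term. The only BY variable is the imputation number.

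SAP 5.5.1 codes four treatment levels: RD-X19 as 1 and 2, "and 3 for Sham from Final Cohort, 4 for Sham from Cohort A".

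On the role of these data, SAP 5.5.2 states: "All secondary clinical, virologic, and exploratory efficacy endpoints will be summarized using descriptive statistics by visit (as appropriate) for each treatment group". Under Protocol 10.1 the only hypothesis testing in "this study will be carried out for these two endpoints", meaning the two primary endpoints.

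**The concern.** Multiple imputation keeps the uncertainty about a missing value by letting it vary across completed datasets. Averaging the 100 copies first removes that variation. Each filled-in value then sits almost exactly on its regression prediction, with no residual scatter, and the SD of the completed column shrinks. The direction is certain whenever a post-baseline value is missing and earlier visits do not predict it perfectly. Baseline rows are not affected, because subjects without a qualified baseline sample are left out.

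The treatment wording is a separate matter. Imputing within each arm needs no dummy variables, whereas three dummies imply one joint model over four groups. The printed code matches neither. Two programmers could follow the text faithfully, with the same fixed seeds, and produce different tables.

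At stake are the spread shown in descriptive tables and their reproducibility. SAP 3.1 says the expansion is partly meant to prepare for future trials. Anyone planning from these SDs would therefore start from a variance that is somewhat too small.

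**Working it through.** The documents state no viral-load SD, visit correlation or missing-sample rate, so there is no plan figure to reproduce. Missingness m and predictability are assumed and shown as ranges.

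**1. Closed form.** Let R² be the share of a visit's log10 variance explained by earlier visits, and M = 100 (SAP 5.5.2). A single imputed draw has about the full variance. The mean of M draws has variance share R² + (1 − R²)/M. Mixing a fraction m of such values with observed ones, and ignoring parameter uncertainty and informative missingness, gives

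SD ratio = √[1 − m(1 − R²)(1 − 1/M)].

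Example with m = 0.20 and R² = 0.5: 0.20 × 0.5 × 0.99 = 0.099, and √0.901 = 0.949.

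| Missing | R² = 0 | 0.25 | 0.5 | 0.75 |
|---|---|---|---|---|
| 5% | 0.975 | 0.981 | 0.988 | 0.994 |
| 10% | 0.949 | 0.962 | 0.975 | 0.988 |
| 20% | 0.896 | 0.923 | 0.949 | 0.975 |

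**2. Simulation of the averaging rule.** The settings were four arms of 120/20/60/10, five visits, an assumed SD of 2 log10, compound-symmetric (0.4, 0.8) or AR(1) (0.4, 0.7) correlation, monotone dropout, Bayesian monotone-regression imputation with 100 copies, and 300 datasets per setting. The figures are Day 14 SD divided by full-data SD for Final Cohort RD-X19.

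| Missing | By arm | Treatment indicators |
|---|---|---|
| 5% | 0.976–0.992 | 0.976–0.992 |
| 10% | 0.951–0.986 | 0.951–0.986 |
| 20% | 0.902–0.968 | 0.900–0.968 |

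For an SD of 2.0, the by-arm shortfalls are 0.02–0.05, 0.03–0.10 and 0.06–0.20 log10. Squaring the ratios gives a variance 2–5% too low at 5% missing and 6–19% too low at 20%. The log10 mean changes by less than 1e-14. A separate simulation with AR(1) 0.3 and 0.6 and n = 60 or 120 gave 0.951–0.958 at 10% and 0.901–0.916 at 20%, consistent with these.

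**3. SD computed within each completed dataset instead.** With treatment indicators in both calls, the ratio is 0.999–1.011 in all four tabulated columns at 5–20% missing. With the SAP's substitution values for undetermined and below-LOQ results (detection limits and Day 14 means assumed), it is 0.992–1.015. Run by arm, the large arms are close to 1, but the small Cohort A arms overshoot:

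- Cohort A RD-X19 (n = 20): 1.036–1.094 at 20% missing.
- Pooled Sham: median ratio 1.034–1.095 at 20%. The sham arm of 10 gave unstable fits there, and 25 of 1,200 datasets could not be fitted.

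Indicators assume a common covariance. If the true SDs were 1.5 (RD-X19) and 2.5 (sham), at 20% missing the SD would be 1.9–6.1% too large for Final Cohort RD-X19 and 0.9–3.2% too small for Pooled Sham.

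**4. Treatment in the imputation model.** The settings were two visits, correlation 0.5, arms of 120:60, a true difference of −1.0 log10 and 20 imputations. The Monte Carlo SE is about 0.02.

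| Missing | By arm | Indicators | No treatment term, arms pooled |
|---|---|---|---|
| 10% | −1.01 | −0.97 | −0.89 |
| 20% | −0.98 | −1.01 | −0.82 |

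The last column is as expected. With balanced baselines the imputed values carry no arm difference, so the contrast is about (1 − m) × (−1.0), which is −0.90 and −0.80.

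**Limits.** Only monotone dropout was simulated, so the MCMC step for intermediate gaps was not exercised. Under that pattern Day 14 has the most missing data, so Days 3, 5 and 8 lose less.

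**The case against.** The best defence is that almost nothing rests on these SDs. The shells carry no standard error, interval or p-value, and clearance is not imputed because a missing swab counts as failure. If missingness and R² are equal across arms, the SDs also shrink by the same proportion. All of this stands, and it keeps the point minor. A reader might infer that a viral-load comparison or the trial's conclusion is biased. The documents do not support that, since testing is confined to the primary endpoints and averaging leaves the means alone.

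The second defence is that the printed code is a template: the seeds are placeholders and one block serves both specimen types. This also stands. A reader might infer that arm differences will be pulled toward zero. That follows only if the code is run as printed on pooled arms, and the prose says otherwise. By-arm and indicator imputation agree closely under the averaging rule, so the conflict is one of wording to reconcile.

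Third, the size is assumed. That is true of the size but not of the direction. Several shortcuts to a firmer figure fail:

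- The 20% dropout in SAP 3.3 covers only discontinuations and hospitalisations. It is not a ceiling, because SAP 5.5.2 also sets invalid, inconclusive and RNase P-undetermined samples to missing.
- Dropout does not equal a missing Day 14 sample either, because SAP 5.1 re-allocates early-termination visits to scheduled time points.
- The absence of discontinuations in EB-P12-01 (Protocol 4.1) says nothing about failed samples.
- The shells print one decimal, but SAP 5.1 generally gives SDs two more decimals than the raw data, so rounding cannot be relied on to hide the effect.

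A reader might also expect distorted medians or a narrowed range. Median shifts were at most 0.02 log10 in the RD-X19 columns with at least 120 subjects. With the substitution values, the averaged-copy minimum can fall below the observed one. Neither claim is made.

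**Conclusion.** Wrong as written, minor, and confined to descriptive tables. The averaging rule understates the log10 SD of nasopharyngeal and saliva viral load at every post-baseline visit with missing samples. Taking the closed form and the simulations together, the Day 14 SD is about 1–2% too small at 5% missing, 1–5% at 10% and 2–10% at 20%. Those figures rest on assumed missing rates and visit correlations, on dropout unrelated to the unobserved value, and on the larger arms. Confidence is high on direction and moderate on size.

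The inconsistent treatment specification is a reproducibility defect and needs reconciling. It does not by itself show bias. Nor do the documents establish that by-arm imputation is the wrong model. Its overshoot in the small arms appears only once SDs are computed within datasets, and the indicator alternative has its own cost when arm variances differ.

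**What to change.** 1. Delete the averaging sentence in SAP 5.5.2 and the matching table footnotes. Either compute the summary statistics within each of the 100 completed datasets and average them across datasets, or report the SD from observed data with the observed N.
2. Take minimum and maximum from observed data and say so in a footnote. Imputed values can fall below the floor of log10 = 0 that SAP 5.5.2 sets for undetermined results.
3. Make prose, code and fallback describe one treatment specification, and do not run the printed code on pooled arms without a treatment term. Indicators in both PROC MI calls are workable and avoid the overshoot in the planned Cohort A arms of 20 and 10, but they assume a common covariance. The choice is the sponsor's and should be stated.
4. If the Final-Cohort-only fallback is used, show the Cohort A and pooled columns on observed data and label them, so that imputed and unimputed subjects are not mixed.

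The cost is SAP wording, footnotes and a few lines of SAS before unblinding. Restoring the Final Cohort RD-X19 SD would raise it by about 1–2.5% at 5% missing (1/0.992 = 1.008 to 1/0.976 = 1.025) and 3–11% at 20% (1/0.968 = 1.033 to 1/0.902 = 1.109). Removing the averaging changes no mean, clearance proportion or primary test.

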6.1 Inclusion Criteria

A subject must meet all the following criteria to be eligible for **inclusion** in this study:

1. Positive for SARS-CoV-2 as detected using an FDA authorized SARS-CoV-2 antigen test at or within 24 hours of the screening visit.
2. COVID-19 signs and symptoms within 72 hours from symptom onset, including at least two moderate* or greater symptoms from: cough, sore throat, nasal congestion, headache, unexplained chills and/or sweats, myalgia, fatigue, nausea (with or without vomiting).
 - Subjects with the presence of at least one moderate symptom and either a) a fever with an oral temperature of at least 100.5 °F or b) shortness of breath/difficulty breathing on exertion (e.g., walking, going up and down stairs) are also eligible for enrollment.

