9.3 Efficacy Assessments

Various outcome assessments will explore the impact of each dose of RD-X19 treatment compared to sham on the sustained resolution of clinical signs and symptoms (in all subjects, and separately in all mild subjects), COVID-19 clinical outcomes, and the \log_{10} reduction of SARS-CoV-2 viral load.

The primary efficacy outcomes are:

- Sustained resolution of COVID-19 signs and symptoms in all subjects (with Mild or Moderate disease at baseline)
- Sustained resolution of COVID-19 signs and symptoms in subjects with Mild disease at baseline

Subjects will be instructed to fill out a diary card or electronic equivalent to assess their signs and symptoms of disease twice daily. Each of the eight symptoms will be rated on a scale from none (0) to severe (3).

Success on sustained resolution will be recorded as at the time (in hours) when cough, sore throat, nasal congestion, headache, chills and or sweats, myalgia, fatigue, and nausea (with or without

vomiting) have been assessed by the subject as none (0) or mild (1) and all symptoms remain at or below 1 until study Day 14.

*Subjects reporting a persistent fever via oral temperature of 100.5 (36 hours or more) or SpO₂ levels <96% with shortness of breath fail to meet the success criterion on that day even if all other symptoms are reported as none (0) or mild (1).

Additional secondary efficacy outcomes include:

- Proportion of study subjects who achieve Day 8 Composite Resolution defined as both a negative SARS-CoV-2 antigen test within the window for Visit 4 (Days 7 – 9) and all symptoms assessed by the subject as none (0) or mild (1), absence of fever and SpO₂ ≥96% without shortness of breath at study day 8 (as reported on the Diary Card Day 8-Assessment 1).
- Proportion of study subjects who experience worsening of COVID-19 disease as defined by an increase of the composite COVID-19 severity score greater than baseline at any point in the study on or after day 3.
- Proportion of study subjects who affirm they have returned to Pre-COVID Health at day 8 and day 14.
- Proportion of study subjects progressing to “severe” clinical outcomes associated with COVID-19.
- Mean change in nasopharyngeal SARS-CoV-2 viral load from baseline on days 3, 5, 8, and 14 by RT-qPCR
- Proportion of subjects demonstrating clearance of viral infection, defined as a negative nasopharyngeal swab via RT-qPCR on each of Days 3, 5, 8 and 14.

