Subjects with multiple exclusion reasons are presented under each category of Reason for Exclusion as appropriate.

For all analysis populations subjects are summarized under the treatment received

Source: Listing 16.x.x

O:\Studies\EmitBio\EB-P20-01\Biometrics\Programs\Tables\xxx.sas ran on Month Day, Year at hh:mm on data from Month Day, Year.

Table 14.1.3 – Demographic and Baseline Characteristics for Safety/Full Analysis Set

	RD-X19 from Final Cohort	RD-X19 from Cohort A	Pooled RD- X19	Pooled Sham	Total
Age (Years)					
N	XX	XX	XX	XX	XX
Mean ± SD	XX.X ± XX.X	XX.X ± XX.X	XX.X ± XX.X	XX.X ± XX.X	XX.X ± XX.X
Median	XX.X	XX.X	XX.X	XX.X	XX.X
Min, Max	XX, XX	XX, XX	XX, XX	XX, XX	XX, XX
Gender n (%)					
Male	XX (XX.X)	XX (XX.X)	XX (XX.X)	XX (XX.X)	XX (XX.X)
Female	XX (XX.X)	XX (XX.X)	XX (XX.X)	XX (XX.X)	XX (XX.X)
Ethnicity n (%)					
Hispanic or Latino	XX (XX.X)	XX (XX.X)	XX (XX.X)	XX (XX.X)	XX (XX.X)
Not Hispanic or Latino	XX (XX.X)	XX (XX.X)	XX (XX.X)	XX (XX.X)	XX (XX.X)
Not Willing to Provide	XX (XX.X)	XX (XX.X)	XX (XX.X)	XX (XX.X)	XX (XX.X)
Race n (%)					
American-Indian or Alaska Native	XX (XX.X)	XX (XX.X)	XX (XX.X)	XX (XX.X)	XX (XX.X)
Asian	XX (XX.X)	XX (XX.X)	XX (XX.X)	XX (XX.X)	XX (XX.X)
Black or African-American	XX (XX.X)	XX (XX.X)	XX (XX.X)	XX (XX.X)	XX (XX.X)
Native Hawaiian or Other Pacific Islander	XX (XX.X)	XX (XX.X)	XX (XX.X)	XX (XX.X)	XX (XX.X)
White or Caucasian	XX (XX.X)	XX (XX.X)	XX (XX.X)	XX (XX.X)	XX (XX.X)
Other	XX (XX.X)	XX (XX.X)	XX (XX.X)	XX (XX.X)	XX (XX.X)
Body Mass Index (kg/m  )					
N	XX	XX	XX	XX	XX
Mean ± SD	XX.X ± XX.X	XX.X ± XX.X	XX.X ± XX.X	XX.X ± XX.X	XX.X ± XX.X
Median	XX.X	XX.X	XX.X	XX.X	XX.X
Min, Max	XX, XX	XX, XX	XX, XX	XX, XX	XX, XX
COVID-19 Composite Severity Score[1]					
N	XX	XX	XX	XX	XX
Mean ± SD	XX.X ± XX.X	XX.X ± XX.X	XX.X ± XX.X	XX.X ± XX.X	XX.X ± XX.X
Median	XX.X	XX.X	XX.X	XX.X	XX.X
Min, Max	XX, XX	XX, XX	XX, XX	XX, XX	XX, XX
Lab confirmed SARS-CoV-2 in nasopharyngeal sample n (%)					
Yes	XX (XX.X)	XX (XX.X)	XX (XX.X)	XX (XX.X)	XX (XX.X)
No	XX (XX.X)	XX (XX.X)	XX (XX.X)	XX (XX.X)	XX (XX.X)
Baseline Disease Severity n (%)					
Mild	XX (XX.X)	XX (XX.X)	XX (XX.X)	XX (XX.X)	XX (XX.X)
Moderate	XX (XX.X)	XX (XX.X)	XX (XX.X)	XX (XX.X)	XX (XX.X)

Baseline Serostatus n (%)					
Antibody (+)	XX (XX.X)				
Antibody (-)	XX (XX.X)				
Nasopharyngeal viral load					
N	XX	XX	XX	XX	XX
Mean $\pm$ SD	XX.X $\pm$ XX.X				
Median	XX.X	XX.X	XX.X	XX.X	XX.X
Min, Max	XX, XX				

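### Viral clearance (SAP 5.5.2) is judged without requiring detectable nasopharyngeal virus at baseline, so a subject already undetermined on Day 1 counts as cleared whenever a later swab is still undetermined.

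*SAP*

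**What the plan says.** Protocol 9.3 lists the endpoint as "Proportion of subjects demonstrating clearance of viral infection, defined as a negative nasopharyngeal swab via RT-qPCR on each of Days 3, 5, 8 and 14". SAP 5.5.2 makes this operational: "clearance of viral infection post baseline visit is defined as achievement of" two conditions at the visit itself, an RNase P Ct of at least 0 and an average N1 Ct that is undetermined. A missing or violated nasopharyngeal sample at a post-baseline visit counts as failure.

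The only baseline condition for the virologic analyses, also in SAP 5.5.2, is that "subjects without a Baseline biospecimen collected and/or the Baseline biospecimen determined to NOT be an analysis-qualified sample, will be excluded". Qualification concerns sample handling, not the result: "Analysis-qualified samples are defined as nasopharyngeal and saliva SARS-CoV-2 biospecimen samples that have no sample Violations". An undetermined viral load in a qualified sample is a valid result, for which "value 1 will be used to calculate descriptive statistics".

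The virologic entry criterion in Protocol 6.1 is "Positive for SARS-CoV-2 as detected using an FDA authorized SARS-CoV-2 antigen test at or within 24 hours of the screening visit". The RT-qPCR is done later at a central laboratory (Protocol 9.1.3). SAP Section 4 sets no PCR condition for the FAS, for the mFAS (which conditions on antibodies) or among the listed PP exclusions. The baseline shell, Table 14.1.3, has a row headed "Lab confirmed SARS-CoV-2 in nasopharyngeal sample n" with Yes and No categories.

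**The concern.** The endpoint is named clearance of viral infection. On this assay, a subject with no detectable nasopharyngeal virus on Day 1 has nothing to clear, yet the rule can score that subject as a success from Day 3 onward. The plan takes the cautious side for missing and violated samples by scoring them as failures, but it has no rule for this opposite case.

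Two things are at stake in Tables 14.2.4.1 and 14.2.4.2. The level of clearance may be overstated, most likely at the early visits, when few baseline-positive subjects will have cleared. The contrast between groups mixes clearance with the share who were undetermined at the start. That share is equal across groups only on average, and one displayed group is small.

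**Working it through.** The documents state no clearance rate, sample size or power for this endpoint, so there is no figure of the plan's own to reproduce. The check uses a mixture identity with three quantities, all assumed:

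- b: share of subjects undetermined at baseline.
- q: chance that such a subject is undetermined at the later visit.
- p: clearance rate in subjects with detectable virus at baseline.

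**1. Reported rate in one group.** Reported = b×q + (1−b)×p. The bias is b×(q−p), which is upward only when q > p. With p = 5% (assumed for Day 3):

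| b | q = 1 | q = 0.5 |
|---|---|---|
| 5% | 0.05 + 0.0475 = 9.75%, about 9.8% | 0.025 + 0.0475 = 7.25%, about 7.3% |
| 10% | 0.10 + 0.045 = 14.5% | 0.05 + 0.045 = 9.5% |
| 20% | 0.20 + 0.04 = 24% | 0.10 + 0.04 = 14% |

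**2. Difference between arms.** If b and q are the same in both arms, the b×q terms cancel and the expected absolute difference is (1−b) times the true one. With p = 60% versus 45% (assumed, true difference 15 points) and q = 1:

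- b = 5%: 62.0% versus 47.75%, difference 14.25 points.
- b = 10%: 64.0% versus 50.5%, difference 13.5 points.
- b = 20%: 68.0% versus 56.0%, difference 12.0 points.

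**3. A late visit where the level falls.** With p = 85% versus 75%, q = 0.5 and b = 10%, the rates become 0.05 + 0.765 = 81.5% and 0.05 + 0.675 = 72.5%. Both are below the true rates, and the difference is 9 points instead of 10.

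**4. Chance imbalance in b.** The number undetermined at baseline was simulated in each arm (200,000 draws, p = 60% versus 45%, q = 1). The ranges reflect only that imbalance, not sampling error in clearance.

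- 120:60 (2:1 split of the Final Cohort's 180), b = 5%: mean 14.25 points, 95% range 10.6 to 17.3. The difference exceeds the true 15 points in about 35% of draws.
- 20:10 (the initial cohort size), b = 10%: mean 13.5 points, 95% range 0.5 to 23.0.

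The second case is a within-cohort comparison. Tables 14.2.4.x show Pooled Sham, which steadies the sham side. The small displayed group is Cohort A RD-X19, with a target of 20 seronegative subjects. There, one baseline-undetermined subject who stays undetermined moves the rate by (1 − 0.05)/20 = 4.75 points at p = 5%.

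**The case against.** The strongest reply is that the SAP does what the protocol asks. Protocol 6.4 glosses the endpoint as undetectable viral load and Protocol 9.3 defines it as a negative swab on each day. SAP 5.5 makes the FAS the primary population for secondary endpoints. The proportion PCR-negative by visit in all treated subjects is an interpretable status measure, and restricting the denominator changes the estimand. That stands, and it is a reason to keep the all-subject table. It also means that a reader should not infer that the endpoint has stopped measuring anything useful.

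A reader might infer that every baseline-undetermined subject is a success from Day 3. The text does not support this. Each visit is judged on its own swab, and a detectable, missing or violated sample is a failure. All subjects were recently antigen-positive and early in their symptoms, so a later detectable swab is plausible.

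A reader might also take the Yes/No row in Table 14.1.3 as proof that the sponsor expects PCR-negative subjects. It only allows for them. The row also works in the plan's favour, because it shows baseline PCR status in the same treatment columns as the clearance tables, so an imbalance in the FAS would be visible. It does not do so for the mFAS, PP or mild-only versions.

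Finally, no decision depends on this endpoint. Protocol 10.1 confines hypothesis testing to the two primary endpoints, and the expected shift is toward no difference when b and q are equal across arms. This limits the weight of the point but does not close the gap.

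**Conclusion.** The gap is real and minor. Nothing in either document requires detectable nasopharyngeal virus at baseline before a subject can count as having cleared it.

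The size depends on b, which the documents do not give. Because entry requires a positive antigen test, b may be small, and at 5% the expected absolute difference loses only one twentieth of its value.

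Two stronger readings should be avoided. Inflation is not general: it requires q > p, which is most likely at Days 3 and 5 and can reverse by Day 14. Shrinkage of the treatment difference is not assured in the realised trial. It is an expectation on the absolute scale with b and q equal across arms. Randomisation supports equal b on average, but q could differ if the device affects later swabs, and chance imbalance in b can push the difference either way. The primary analyses and their type I error are untouched.

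**What to change.** Before unblinding, state in SAP 5.5.2 and in the notes to Tables 14.2.4.1 and 14.2.4.2 that the main clearance denominator is subjects with detectable N1 in an analysis-qualified baseline nasopharyngeal sample. Keep the all-subject version as a sensitivity analysis. Report the number undetermined at baseline by group for each population tabulated.

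The filter uses a pre-treatment result that is already collected, so it does not compromise the randomised comparison, and it returns p in each group. The cost is a short SAP text change, a slightly smaller denominator, and a small departure from the full FAS for this endpoint, which the sensitivity table covers. Setting the rule before unblinding matters because a denominator chosen afterwards would look data-driven.
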